¹ The daily dosing log in the Caregiver Diary will be reviewed at all post-baseline visits through EOT. If any doses are missed or mis-dosed, this should be queried with the caregiver and appropriate feedback given to the family. This feedback should be documented in the source documents. At the in-home nurse visit, the nurse will review the caregiver diary to check any issues and provide feedback to the family at the visit. The nurse will notify the site about any urgent issues the day of the visit and note anything else in the source documents. The nurse does not sign the daily dosing log/summary page. The source documents and the diary will be sent to the site. The Investigator (or appropriately credentialed delegee) will review the diary and source documents collected at the in-home visit.

^m Coagulation includes prothrombin time, activated partial thromboplastin (aPTT), and international normalized ratio (INR).

ⁿ A Comprehensive Metabolic Panel will be assessed every post-enrollment visit (see Section 9.5.2). If abnormal findings are observed on renal or liver function tests, additional tests as is clinically indicated may be conducted as described in Sections 9.5.2.1 and 9.5.2.3).

^oBoth urinalysis and a urine screen for drugs of abuse will be evaluated at Screening (See Section 9.5.2).

^p For female subjects who have reached menarche.

^q See Table 2 and Table 3 for PK blood collection times.

^r The Mullen is done for subjects who cannot obtain basal on SB5 or for whom the SB5 is developmentally inappropriate.

^s The study exit form should also be completed if the subject terminates the study early.

Table 2 Pharmacokinetic Blood Sampling Schedule (Subjects Ages 7 to 12 Years Old)

Week	Visit No.	Treatment	Timing of Sample (relative to start of dosing) ^a	Sample Time Point
2	5		Pre dose (-120 to -15 minutes) ^b	1
			1-3 hours post dose ^c	2
			4-7 hours post dose ^c	3
6	9	Mid-treatment	Pre dose (-120 to -15 minutes) ^b	4
			1-3 hours post dose ^c	5
			4-7 hours post dose ^c	6
13	16	End of Treatment	Pre dose (-120 to -15 minutes) ^b	7
			1-3 hours post dose ^c	8
			4-7 hours post dose ^c	9

^a All post-dose windows are determined from the first dose of the visit (morning dose) and all PK samples must be collected before the second dose (PM dose).

^b Pre dose counts as both T0 and 12 hours post dose from previous evening (near trough). The previous evening's dose should be taken in the evening as late as possible, preferably before bedtime.

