9.2.17 Visit 17 Follow-up (telemedicine and in-home) – Week 15 (+ 4 days)

Visit 17 (Week 15, Follow-up) will be a combined remote telemedicine and in-home visit. The assessments to be conducted and data collected are divided accordingly below.

Remote/Telemedicine - Investigator and Appropriate Site Staff

The remote visit will be conducted by the site via telemedicine or video facilities as appropriate. Caregiver assessments must be completed the day of the visit or no earlier than the day before the visit (except the caregiver diary which is completed daily) and reviewed by the Investigator.

The Investigator will also query changes in tolerability and note any changes. The Investigator is responsible for determining and reporting any changes that qualify as AEs.

The following assessments will be conducted, and data collected or reviewed by site personnel during Follow-up:

- Safety
 - Recent clinical history
 - Physical and neurological examination: A modified version of the physical and neurological exam will be done based on the guidance document provided to the Investigator.
 - Review for AEs/SAEs
- Review Caregiver Diary (con-meds, seizures, voids, oral intake changes in symptoms)
- Efficacy
 - o CGI-I
 - CGI-S
 - Caregiver Top 3 Concerns
 - o ABC-2
 - o CSHO
 - o GIHQ
- Study Exit Form

In-home Nurse Visit

The in-home visit will be conducted by a visiting nurse who will also query any changes in tolerability during the in-home visit. Any changes will be noted and provided to the Investigator.

The following assessments will be conducted and data collected by the home nurse during Follow-up:

- Review for AEs/ SAEs
- Review caregiver diary: concomitant medications, voids, oral intake, changes in symptoms
- Vital signs
- Weight
- Collect blood samples:
 - CBC with differential
 - Coagulation
 - CMP
- Collect urine for urinalysis
- 12-lead ECG
- Targeted Physical Exam: general appearance, abdominal, CVA tenderness, check for edema. Exam may include a suprapubic exam (bladder palpation) to assess for urinary retention if decreased urine output is noted.

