Subjects who have received IMP for longer than 2 weeks and discontinue prematurely any time after Visit 5 should return to the investigational site for final safety and efficacy assessments as scheduled for the EOT visit (Visit 16) and complete the study exit form.

Neuren Pharmaceuticals Ltd.	Clinical Trial Protocol	Version 3.0
Confidential	Neu-2591-PMS-001	October 30, 2023

Subjects who discontinue from the trial prior to receiving any treatment or who discontinue after having received treatment only up to Visit 5 may be replaced.

Subjects with early treatment cessation due to SAEs must be followed-up and provided appropriate medical care until their signs and symptoms have remitted or stabilized, or for the remaining study period (until study end), whichever comes sooner. "Study end" is when all subjects have finished the study.

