10.8.3 Follow-up of AEs and SAEs

After the initial AE/SAE report, the Investigator is required to proactively follow each subject and provide further information to the Sponsor on the subject's condition.

All AEs and SAEs documented at a previous visit/contact and are designated as ongoing, will be reviewed at subsequent visits/contacts.

All AEs will be followed until resolution, until the condition stabilizes, or until 30 days after the subject's Follow Up visit (Visit 17). At which time, the appropriate AE/SAE eCRF page(s) will be updated. SAEs and g. renal AEs that are ongoing at the Follow-up visit (Visit 17) will be followed until resolution, stabilization of subject condition, or study end, whichever occurs first. In such cases, follow-up Serious Adverse Event (RAER) forms will be completed at the Follow-up visit (Visit 17) as well as completed upon resolution, stabilization, or study end, whichever occurs first. "Study end" is when all subjects have completed the study.

The Investigator will ensure that follow-up includes any supplemental investigations as may be indicated to elucidate the nature and/or causality of the AE or SAE. This may include additional laboratory tests or investigations, histopathological examinations, or consultation with other health care professionals.

The Sponsor may request that the Investigator perform or arrange for the conduct of supplemental measurements and/or evaluations to elucidate as fully as possible the nature and/or causality of the AE or SAE. The Investigator is obligated to assist. If a subject dies during participation in the study or during a recognized follow-up period, the Sponsor will be provided with a copy of the death certificate and any post-mortem findings, including histopathology.

New or updated information will be recorded on the originally completed SAE or Renal Adverse Event form, with all changes signed and dated by the Investigator. The updated SAE form should be resent to the Sponsor within the time frames outlined below in Section 10.8 Prompt Reporting of the SAEs to the Sponsor.

Any clinical adverse event that is serious (as defined above in Section 10.2)

occurring during the course of the study, irrespective of the treatment received by the subject, must be reported to the Sponsor and Sponsor's agent within 24 h (or sooner if possible) of the Investigator or designee becoming aware of the situation.

Neuren Pharmaceuticals Ltd.	Clinical Trial Protocol	Version 3.0

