SAEs that are ongoing at the Follow-up visit (Visit 17) will be followed until resolution, stabilization of subject condition, or study end, whichever occurs first. In such cases, follow-up SAER forms will be completed at the Follow-up visit (Visit 17) as well as completed upon resolution, stabilization, or study end, whichever occurs first. "Study end" is when all subjects have completed the study.

All SAE and AE data will be reviewed by the DSMC at scheduled meetings.

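### Follow-up of ongoing SAEs is capped at study end with no 30-day floor, so in the last children to finish the SAE rule may require less follow-up than the rule for all AEs

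*Protocol*

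**What the plan says.** Three protocol sections bear on how long an unresolved event is followed.

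- **Section 10.8.3, general rule.** "All AEs will be followed until resolution, until the condition stabilizes, or until 30 days after the" child's own Visit 17. The next sentence has the AE/SAE pages of the eCRF updated at that time.
- **Section 10.8.3, SAE rule.** SAEs ongoing at Visit 17 (and, as far as the damaged public text shows, renal AEs) "will be followed until resolution, stabilization of subject condition, or study end, whichever occurs first". A follow-up form is completed at Visit 17 and again when the first of those three points is reached.
- **Section 10.9.1.** The SAE rule is repeated in the same terms. Study end "is when all subjects have completed the study".
- **Section 9.4.5.** Subjects whose treatment stopped early because of an SAE "must be followed-up and provided appropriate medical care until their signs and symptoms have remitted or stabilized". The section then gives an alternative limit, namely "for the remaining study period (until study end), whichever comes sooner". Here study end "is when all subjects have finished the study".

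Section 10.1 makes SAEs a subset of AEs. No visible sentence says which limit prevails when the two differ. The SAP sets no SAE follow-up limit.

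Study end is not tied to a dated event. The indirect evidence is that Section 9.2.17 lists the "Study Exit Form" at Visit 17, and a footnote to Table 1 adds: "The study exit form should also be completed if the subject terminates the study early". In addition, Section 7.4 ends the timeline at the Week 15 follow-up, and SAP Section 4.3 counts days in the study to the last visit.

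**The concern.** The two limits run on different clocks. The AE limit is 30 days from each child's own Visit 17. The SAE limit is a calendar event shared by the whole cohort. For a child who finishes early, the shared event comes later and the SAE rule is the more generous one. For a child who finishes near the end, the order can reverse, and the serious event then has the shorter required follow-up.

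What could be lost is the final outcome, and any revised causality, of an SAE that is neither resolved nor stable when a late finisher leaves. Section 10.8.2 expects causality to be revisited in the light of follow-up information. The cap in Section 9.4.5 also covers the medical care owed to a child whose treatment was stopped for an SAE. Safety is the primary objective, and this is the drug's first study in this population. Enrolment is staggered from the oldest group to the youngest, so the late finishers may include the youngest children.

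**Working it through.** The plan gives no figure of its own to reproduce. The check compares the two limits and does the date arithmetic.

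**Inputs from the documents**
- AE limit: 30 days after own Visit 17 (10.8.3).
- SAE limit: study end (10.8.3, 10.9.1, 9.4.5).
- Visit 17: Week 15 (+4 days), that is Day 105 to Day 109 (9.2.17).
- Last permitted dosing day: Day 91 (9.4.2).
- About 20 children (7.1).

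**Assumptions**
- Study end is the last subject's Visit 17, and the specific SAE sentence governs.
- Children complete evenly at 1 to 4 per 30-day month. The documents give no rate.
- A proportion p of 1% to 5% of children have an SAE neither resolved nor stabilised at Visit 17. The documents give no rate, and renal AEs are not counted.

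**Step 1: the limits after Visit 17.** Let d be the days from a child's Visit 17 to the last child's Visit 17. The SAE limit is d and the AE limit is 30. The shortfall is 30 − d when d < 30, and otherwise 0.
- Last child, d = 0: SAE 0 days, AE 30 days.
- d = 14: SAE 14 days, AE 30 days.
- d ≥ 30: the SAE limit is equal or longer.

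**Step 2: the last child, counted from a last dose on Day 91.**
- SAE limit: 105 − 91 = 14 to 109 − 91 = 18 days.
- AE limit: 14 + 30 = 44 to 18 + 30 = 48 days.

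These figures hold only for a child dosed to Day 91. Section 9.4.5 requires dosing to stop for any SAE considered related. After such a stop the last dose is earlier, and a Visit 17 held on schedule falls more than 14 to 18 days after it.

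**Step 3: children in the window (k, with d < 30).**

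| Completions per month | d (days) | Shortfalls (days) | k | Mean shortfall (days) |
|---|---|---|---|---|
| 1 | 0 | 30 | 1 | 30 |
| 2 | 0, 15 | 30, 15 | 2 | 22.5 |
| 4 | 0, 7.5, 15, 22.5 | 30, 22.5, 15, 7.5 | 4 | 18.75 |

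For the other 16 to 19 of 20 children the study-end limit is equal or longer.

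**Step 4: children affected.** The expected number is k × p, from 1 × 0.01 = 0.01 to 4 × 0.05 = 0.20. The chance of at least one is 1 − (1 − p)^k, from 0.01 to 1 − 0.95^4 = 0.185.

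**Step 5: with the fix.** The limit becomes the larger of d and 30 days. The last child goes from 0 to 30, a child with d = 14 goes from 14 to 30, and a child with d ≥ 30 is unchanged.

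**The case against.** The best answer is that no time is lost. The 30-day sentence covers all AEs, SAEs are AEs under Section 10.1, and the very next sentence has SAE pages of the eCRF updated at the 30-day point. On that reading every SAE gets at least the 30-day limit, and the study-end sentence adds time for events still open. That the study-end limit is equal or longer for most children fits this intention. This reading is plausible and may be what the authors meant. It does not fully settle the matter: the specific SAE sentence takes the earliest of its three limits and closes the SAE form there, and Sections 9.4.5 and 10.9.1 show no 30-day limit at all. On this reading, what remains is the closing date of the SAE form.

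Second, equating study end with the last Visit 17 is an inference. The exit form, the one-line timeline and a descriptive SAP derivation define nothing. If study end includes the 30 days, the shortfall is zero. That stands, and it is why the point is conditional.

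Third, other duties have no stated end date: proactive follow-up and help with sponsor-requested evaluations (10.8.3), and forwarding SAE information as it becomes available (10.9.1). They make silent loss less likely, but they do not set a minimum period. Parts of the renal and safety text are also not visible in the public copy, so a separate rule there cannot be excluded.

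A reader might infer that SAEs in this trial are followed for less time than non-serious AEs, or that the safety results are biased. The documents support neither. The reversal is conditional and confined to the last finishers, and incidence is counted to the last study visit (6.3.1.1) whichever limit applies.

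**Conclusion.** The point holds as a minor one. As written, the study-end cap has no 30-day floor in any of the three sections. If study end is the last Visit 17 and the specific SAE sentence governs, the required follow-up of an unresolved, unstabilised SAE falls below 30 days for children finishing within 30 days of the last child, and to 0 days for the last child. If either condition fails, no follow-up time is lost.

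On the assumed rates the window holds 1 to 4 of 20 children, the expected number affected is 0.01 to 0.2, and the chance of any is 1% to 19%. Probably no child or one child would be affected. Incidence, sample size, power and type I error are untouched. It would be wrong to apply the contrast of 14 to 18 against 44 to 48 days after the last dose to all SAEs, because it does not fit those that stopped treatment early.

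**What to change.** In Sections 10.8.3, 10.9.1 and 9.4.5, follow ongoing SAEs to resolution or stabilisation or, failing that, to the later of study end and 30 days after the subject's Visit 17 (or last visit, if Visit 17 is not done). Apply the same limit to renal AEs unless a renal rule in the non-visible text already does so. It would help to define study end by a dated event, such as the last subject's Visit 17, but the floor is the change that matters.

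The cost is one sentence in three places. No child's follow-up becomes shorter. Database lock may wait up to 30 days after the last Visit 17, which the existing AE rule already implies.

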10.9 Prompt Reporting of the SAEs to the Sponsor

Once an Investigator or delegate becomes aware that an SAE has occurred in a study subject, she/he will report the information to the Sponsor's appointed agent within 24 hrs.

10.9.1 Completion and transmission of the SAE reports

Serious Adverse Events will be processed by the Pharmacovigilance Team at the support of and review by the Medical Monitor and Neuren's Medical Team. A serious adverse event report (SAER) form is to be completed for each SAE occurring up to the final study visit, regardless of causality. This includes renal AEs that meet criteria for an SAE. In addition, the SAE is to be recorded on the appropriate section of the eCRF. The SAER must be submitted to the Pharmacovigilance Team at the email belowwithin 24 hours of the time the SAE is first observed.

The Medical Monitor or pharmacovigilance department will contact the Investigator should it be necessary to clarify any of the event information. The Investigator should provide follow-up information for the event to pharmacovigilance department as soon as it becomes available. If required, the Investigator should report these events to the local IRB.

The SAE form will always be completed as thoroughly as possible with all available details of the event and signed by the Investigator (or authorized designee). If the Investigator does not have all information regarding an SAE, he/she will not wait to receive additional information before notifying the Medical Monitor of the event and completing the form. The form will be updated when additional information is received.

The Investigator will always provide an assessment of causality at the time of the initial report as described in Section 10.7.2 Assessment of Causality.

Any event that in the opinion of the Principal Investigator may be of immediate or potential concern for the subject's health or well-being will be reported to the Pharmacovigilance Team, who will be in copy of Medical Monitor.

In accordance with applicable regulations and local laws, the Sponsor will identify and report within the required time frame to regulatory authorities and Investigators all adverse events assessed as likely drug related that are determined to be both serious and unexpected. Investigators will be responsible for reporting this safety information to their IRB.

Neuren Pharmaceuticals Ltd.	Clinical Trial Protocol	Version 3.0
Confidential	Neu-2591-PMS-001	October 30, 2023

SAEs that are ongoing at the Follow-up visit (Visit 17) will be followed until resolution, stabilization of subject condition, or study end, whichever occurs first. In such cases, follow-up SAER forms will be completed at the Follow-up visit (Visit 17) as well as completed upon resolution, stabilization, or study end, whichever occurs first. "Study end" is when all subjects have completed the study.

All SAE and AE data will be reviewed by the DSMC at scheduled meetings.

10.10 Deaths

A SAER form is to be competed for all deaths. Death will be recorded in the eCRF. Source documentation (e.g., autopsy report, death certificate) to confirm the cause of death will be reviewed by the DSMC.

Page 96 of 117

10.12 Pregnancy

Pregnant, lactating, or breastfeeding females are to be excluded from this study. In the event of pregnancy, it will be reported on a pregnancy form, and will be followed up to determine outcome, including spontaneous or voluntary termination, details of birth, and the presence or absence of any birth defects or congenital abnormalities. The investigator should report all pregnancies in female clinical trial subjects to the **Example 1** Pharmacovigilance Team as soon as possible using the Pregnancy Data Collection Form.

Submit Pregnancy Data Collection form vial email to:

It is not expected that there will be sexually active participants in the study population, and as such some of the provisions that follow may have limited applicability based on the age range of study participants and the nature of the disease under study. These provisions are nonetheless included for purposes of completeness.

Subjects of childbearing potential must abstain from sexual activity for the duration of the study and for at least 30 days thereafter. If a subject is sexually active or becomes sexually active during the study, she or he must use 2 clinically acceptable methods of contraception (e.g., oral, intrauterine device [IUD], diaphragm plus spermicide, injectable, transdermal or implantable contraception, condom use alone (male type only)) for the duration of the study and for at least 30 days thereafter.

11. STATISTICAL PLAN

11.1 Definitions

11.1.1 Subject Populations

For this trial the following populations will be defined and used in the analysis:

Intent-to-treat (ITT) Population

The Intent to Treat (ITT) population consists of all subjects enrolled into the study.

Per-protocol (PP) Population

The PP population is defined as all subjects recruited into the trial who received Investigational Medicinal Product and had no major protocol violations.

Safety Population

The safety population will include all subjects in the ITT population.

Pharmacokinetic (PK) Population

The PK population will include all subjects enrolled in this study who receive the IMP through to the morning dose of Week 2 (Visit 5) as a minimum, and who undergo PK sample collection at the specified post-dose time point(s) through to Week 2 (Visit 5) as a minimum.

11.2 Sample Size Determination

Sample sizes were estimated for this open-label study using within-subject change as the measure of improvement. Given the limited data from interventional trials in these patient populations, and that this is the first clinical study of NNZ-2591 IMP in this population, treatment change estimates were based on Clinical Global Impression Scale of Improvement (CGI-I) data from completed clinical trials in other rare, neurodevelopmental disorders. Based on the information provided in Glaze et al.¹ (Double-blind, randomized, placebo-controlled study of trofinetide in pediatric Rett syndrome), the standard deviation of the CGI-I is approximately 0.7 at a single timepoint. For a sample size of 20 subjects, a two-sided significance level of 0.05, and a Wilcoxon signed-rank test, the study will be able to detect a difference of 0.55 units of change in the CGI-I at a power of 0.90. For a power of 0.80, 0.85, and 0.90, the detectable difference would be 0.48, 0.51, and 0.55 or larger, respectively. The effect size for a power of 0.80, 0.85, and 0.90 is 0.68, 0.73, and 0.79, respectively. If the observed standard deviation is larger, the size of the detectable difference would also be larger. For example, if the standard deviation is 1.45, the detectable difference for a power of 0.80, 0.85, and 0.90 is 1.02, 1.09, and 1.18 or larger, respectively.

11.3 Safety Analyses

Safety analyses will be conducted on the Safety Population and based on the safety endpoints listed in Section 6.3.1. Adverse events and other safety data will be summarized as frequencies and percentages, described in terms of severity and potential attribution. Objective safety assessments will be summarized over time on study; shift tables at time points of interest may be generated. The safety analysis details will be specified in the Statistical Analysis Plan (SAP).

